5.4.1.2.2 PASI75 (Week 4) response

The estimand for the secondary efficacy endpoint PASI75 response at Week 4 is defined as follows:

- **Participant-level outcome:** PASI75 response at Week 4.
- **Treatment:** Bimekizumab high dose (Dose A) and low dose (Dose B).
- **Population:** Study participants enrolled according to the protocol-specified inclusion/exclusion criteria and randomized to IMP.
- **Intercurrent event handling:** An intercurrent event is defined as discontinuation of IMP prior to Week 4. A composite strategy will be implemented in which a positive clinical outcome is defined as achieving PASI75 response at Week 4 and not discontinuing IMP through Week 4.
- **Population-level summary:** Percentage of participants achieving PASI75 response at Week 4 in each dose group.

The PASI75 at Week 4 will be analyzed in the same manner as PASI90 at Week 16.

5.4.1.2.3 IGA 0/1 response (Week 16)

The estimand for the secondary efficacy endpoint IGA 0/1 response at Week 16 is defined as follows:

- **Participant-level outcome:** IGA 0/1 response at Week 16.
- **Treatment:** Bimekizumab high dose (Dose A) and low dose (Dose B).
- **Population:** Study participants enrolled according to the protocol-specified inclusion/exclusion criteria and randomized to IMP.
- **Intercurrent event handling:** An intercurrent event is defined as discontinuation of IMP prior to Week 16. A composite strategy will be implemented in which a positive clinical outcome is defined as achieving IGA 0/1 response at Week 16 and not discontinuing IMP through Week 16.
- **Population-level summary:** Percentage of participants achieving IGA 0/1 response at Week 16 in each dose group.

The number and percentages of IGA 0/1 responders at Week 16 will be reported for each dose group in the same manner as PASI90/PASI75 responder variables. Missing data and intercurrent events will be handled similar to the PASI response variables.

5.4.1.2.4 CDLQI (total score) change from baseline (Week 16)

The estimand of the secondary QOL endpoint CDLQI total score change from Baseline to Week 16 is defined as follows:

- **Participant-level outcome:** Change from Baseline to Week 16 in CDLQI total score.
- **Treatment:** Bimekizumab high dose (Dose A) and low dose (Dose B).
- **Population:** Study participants enrolled according to the protocol-specified inclusion/exclusion criteria and randomized to IMP.
- **Intercurrent event handling:** An intercurrent event is defined as discontinuation of IMP prior to Week 16. A hypothetical strategy will be implemented in which participants with an intercurrent event are treated as though they had completed the randomized IMP through Week 16.
- **Population-level summary:** Mean change from Baseline to Week 16 in CDLQI total score in each dose group.

The change from Baseline to Week 16 in CDLQI total score will be summarized descriptively including n, mean, median, SD, min/max, and lower/upper quartiles in each dose group. The 95% CIs for the mean change will also be provided.

The LOCF method will be used to impute the missing value. The OC method will also be used.

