9.3.2 Secondary efficacy analyses

The secondary efficacy variables will be analyzed for all study participants in the RS by randomized treatment arm.

No formal statistical testing will be conducted for the secondary efficacy variables. Objectives and endpoints related to secondary efficacy analyses are described in Section 3. The estimands related to secondary efficacy analyses are described in Section 9.3.2.1.

A participant will be classified as a PASI90 responder at Week 16 if the PASI score at Week 16 has improved by at least 90% from Baseline.

A participant will be classified as an IGA 0/1 responder if he/she has at least a 2-category improvement from Baseline at Week 16 and the IGA score is Clear [0] or Almost Clear [1].

A participant will be classified as a PASI75 responder at Week 4 if the PASI score at Week 4 has improved by at least 75% from Baseline.

Change from Baseline in CDLQI total score at Week 16 is defined as Week 16 CDLQI total score minus Baseline CDLQI total score.

The binary secondary efficacy variables of PASI90 response at Week 16, IGA 0/1 response at Week 16, and PASI75 response at Week 4 will be summarized descriptively with counts and percentages. Any participant who has missing data for the respective efficacy variable will be classified as a nonresponder for analysis. An observed case (OC) method will also be implemented to assess the impact of the main method of handling missing data.

The continuous efficacy variable change from Baseline in CDLQI response at Week 16 will be summarized descriptively. In addition to the standard set of summary statistics for continuous variables defined in Section 9.2, the upper and lower quartiles will also be reported. Multiple imputation will be used to account for missing continuous data in the analysis. The multiple imputation method will be described in more detail in the SAP. An OC method will be implemented to assess the impact of the main method of handling missing data.

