9.3.3 Other analyses

The other efficacy variables will be analyzed based on the RS for analyses based on the combined Initial Treatment Period and OLE Period. Other efficacy variables will also be analyzed based on the OLS for analyses based on the OLE Period. Other efficacy variables will be summarized descriptively by visit, with counts and percentages for binary (responder) variables and descriptive statistics for continuous variables as defined in Section 9.2. Objectives and endpoints related to other efficacy analyses are described in Section 3.

Binary (responder) variables will be analyzed as done for the binary secondary efficacy variables. Continuous variables will be analyzed as done for the continuous secondary efficacy variable. Further details will be provided in the SAP.

An E-R analysis will be performed to evaluate the relationship between the plasma concentration of bimekizumab and PASI and IGA responses. The analysis may be performed by combining the data from PS0020 and data from adult Phase 2 and 3 studies in PSO to characterize the similarities and differences, if any, between the adult and adolescent participants. The derived model will be used to perform simulations to define the dose and dose regimen for the PS0021 study.

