5.1.1.7.1 Rationale for estimand

Intercurrent events have been identified within the estimands for this study because of their potential to impact efficacy assessments linked with the secondary study objectives. In order to account for the effect of any observed post-randomization intercurrent events on the efficacy analyses, the following estimand strategies will be implemented when evaluating the secondary efficacy endpoints:

- A composite estimand strategy will be used for the analysis of secondary binary endpoints (PASI90 response at Week 16, PASI75 response at Week 4, IGA 0/1 response at Week 16).
- A hypothetical estimand will be used for the analysis of the continuous secondary endpoint (CDLQI total score change from Baseline at Week 16).

The assumptions and robustness of the secondary efficacy analyses involving binary endpoints and the composite estimand strategy will be assessed through the sensitivity analyses defined in Section 5.4.1.3.

5.1.1.7.1.1 Composite estimand

A composite estimand strategy as defined in Section 5.4.1.2 allows incorporation of the intercurrent event (eg, discontinuation of IMP on or before Week 4 or Week 16) within the definition of the secondary efficacy endpoint. This intercurrent event is considered meaningful to the efficacy outcomes following administration of IMP. For example, within the proposed composite estimand framework, a randomized study participant who discontinues from IMP prior to Week 16 will be considered a treatment failure at Week 16 in the analysis of the PASI90 response at IGA 0/1 response analyses regardless of the observed PASI or IGA data.

5.1.1.7.1.2 Hypothetical estimand

The hypothetical estimand strategy is defined in Section 5.4.1.2, and involves a data-driven approach to account for the potential impact of an intercurrent event (eg, discontinuation of IMP

on or before Week 16) on the analysis of continuous secondary efficacy data. Under this framework, outcomes for study participants without an intercurrent event are analyzed as observed. Conversely, outcomes for study participants with an intercurrent event are imputed via the LOCF method a, ie, data which are missing on or after the intercurrent event will be imputed via LOCF following the method described in Section 5.1.1.7.3.

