5.1.1.7.3 Efficacy missing data

An intercurrent event is defined as discontinuation of IMP prior to the time point of interest. For secondary efficacy variables with binary responses, (eg, PASI90 at Week 16, PASI75 at Week 4, and IGA0/1 response at Week 16), study participants who have an intercurrent event will have their efficacy response variable at the timepoint of the intercurrent event and all subsequent timepoints (whether the data were observed or not) set to “nonresponse”. An observed case (OC) analysis will be performed as a sensitivity check.

For secondary continuous efficacy endpoints (CDLQI [total score] change from Baseline at Week 16), the last observation carried forward (LOCF) will be used for participants who have an intercurrent event. The observed cases (OC) method will also be performed. Definitions of intercurrent event and missing data handling specific to each secondary efficacy endpoint are provided in Section 5.4.1.2. Note, the same approach will be used for missing data not preceded by an intercurrent event, ie, LOCF for continuous endpoints and nonresponder imputation for binary endpoints. Baseline measurements are eligible to be carried forward in the event that this is the last available measurement for a participant who is missing post-Baseline data.

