5.5.2 PASI change from baseline

The PASI score values and change from Baseline will be summarized descriptively for each timepoint for the OC.

In addition, the value, change, and percent change from Baseline of percent BSA involvement will be summarized descriptively for each timepoint by dose group in the OC.

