5.5.6 CDLQI 0/1 response over time

The number and percentage of participants who have a CDLQI total score of 0 or 1 will be reported for each time point and by dose group for OC only.

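### LOCF does not fit the hypothetical estimand for Week 16 CDLQI, and observed-case PASI change and CDLQI 0/1 depart from Protocol 9.3.3 without being listed, describing retained participants only after Week 20

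*SAP*

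**What the plan says.** **Week 16 CDLQI.** Protocol 9.3.2.1 and SAP 5.4.1.2.4 state the same hypothetical strategy: "participants with an intercurrent event are treated as though they had completed the randomized IMP through Week 16". The protocol pairs it with multiple imputation: "Multiple imputation will be used to account for missing continuous data in the analysis" (9.3.2). Protocol 9.6 falls back to observed cases if the imputation model does not converge. The SAP keeps the estimand and changes the estimator: "The LOCF method will be used to impute the missing value". SAP 5.1.1.7.1.2 says that "data which are missing on or after the intercurrent event will be imputed via LOCF", and SAP 5.1.1.7.3 adds "Baseline measurements are eligible to be carried forward in the event that this is the last available measurement for a participant" with no post-Baseline data. A 95% CI for the mean change is planned. Appendix 6.2 records the switch from multiple imputation to LOCF and gives no reason. The sensitivity analyses in SAP 5.4.1.3 are observed-case and a PK-PPS summary; neither uses multiple imputation.

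**Endpoints over time.** Protocol 9.3.3 states: "Binary (responder) variables will be analyzed as done for the binary secondary efficacy variables". It treats continuous variables in the same way, by reference to the CDLQI method. For PASI the SAP says: "The PASI score values and change from Baseline will be summarized descriptively for each timepoint for the OC". For CDLQI 0/1 it says the results "will be reported for each time point and by dose group for OC only". Both are protocol endpoints (Section 3). Appendix 6.2 does not mention either change.

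**Week 20.** Protocol 7.2 requires withdrawal of any participant with IGA of 3 or more at Week 20.

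**The concern.** The first issue is a mismatch between question and method. The estimand asks what the Week 16 score would have been on continued treatment. LOCF reports the last score seen, or no change at all when only Baseline exists. If CDLQI is still improving, the mean change is pulled towards zero, and the interval around it treats filled-in values as if they had been measured.

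The second issue concerns long-term reporting. Withdrawal at Week 20 depends on response. A summary restricted to participants still observed after Week 20 therefore leaves out the people who did worst. If one dose group loses more participants at Week 20, its later results improve relative to the other group for that reason alone. A reader would also see NRI-based PASI and IGA response rates beside retained-only PASI change and CDLQI 0/1 at the same visits.

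**Working it through.** There is no planned figure to reproduce: the documents give no dropout rate, expected CDLQI change or Week 20 removal rate. The only documented input is n = 20 per dose group (Protocol 1.1). Everything else below is an assumption.

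**LOCF, general form.** Let D be the mean on-treatment change, k the number of discontinuers (assumed to share D), and f the fraction of D already present in the carried score.

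LOCF mean = [(20 − k)·D + k·f·D] / 20, so attenuation = k(1 − f)/20.

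With assumed D = −8:

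| k | f = 0 (Baseline carried) | f = 0.5 | f = 1 (plateau) |
|---|---|---|---|
| 1 | −7.6 (5%) | −7.8 (2.5%) | −8.0 (0%) |
| 2 | −7.2 (10%) | −7.6 (5%) | −8.0 (0%) |
| 4 | −6.4 (20%) | −7.2 (10%) | −8.0 (0%) |

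**LOCF, worked trajectory.** Assume mean changes of −4, −6, −8 and −9 at Weeks 4, 8, 12 and 16. Three of 20 stop, with last doses at Weeks 0, 4 and 8.

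- Next visit not attended: carried scores are 0, −4 and −6. Loss = (9 + 5 + 3)/20 = 0.85, so the mean is −8.15 instead of −9.0 (9%).
- Next visit attended: it falls 28 days after the last dose, so the score is kept under the 33-day rule in SAP 5.1. Carried scores are −4, −6 and −8. Loss = (5 + 3 + 1)/20 = 0.45, so the mean is −8.55 (5%).

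**Observed-case against NRI after Week 20.** Let w be the number removed and r the later responders. Observed-case rate = r/(20 − w); NRI rate = r/20. With r = 12:

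| w | Observed-case | NRI | Gap (points) |
|---|---|---|---|
| 1 | 12/19 = 63.2% | 60% | 3.2 |
| 2 | 12/18 = 66.7% | 60% | 6.7 |
| 4 | 12/16 = 75.0% | 60% | 15.0 |

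For r from 10 to 14 the gap is 2.6 to 3.7 points at w = 1 and 12.5 to 17.5 points at w = 4. Two dose groups that both have 12 of 20 responders would show 63.2% and 75.0% if one lost 1 participant and the other 4.

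**PASI change after Week 20.** Assume −18 in those retained and −6 in those removed. Observed-case gives −18. All 20 participants would give (18 × −18 + 2 × −6)/20 = −16.8 with 2 removed, or (16 × −18 + 4 × −6)/20 = −15.6 with 4 removed.

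**Which summaries are touched.** The endpoints over time compare as follows:

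| Endpoint over time | Protocol 9.3.3 | SAP |
|---|---|---|
| PASI50/75/90/100 | NRI | secondary-endpoint methods (5.5.1) |
| IGA 0/1, IGA 0 | NRI | secondary-endpoint methods (5.5.3) |
| PASI score and change | multiple imputation | observed-case (5.5.2) |
| CDLQI 0/1 | NRI | observed-case only (5.5.6) |

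SAP 5.5.4 (scalp IGA) and 5.5.5 (CDLQI change over time) name no missing-data method and are not counted here.

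**The case against.** Several stronger readings are tempting, and the documents do not support them.

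- *All endpoints over time are observed-case.* They are not. The PASI responder and IGA response series use the secondary-endpoint methods, including NRI, so the main long-term response rates are protected.
- *The protocol requires NRI for the absolute PASI thresholds.* Those thresholds are an SAP addition and not a protocol endpoint, so observed-case there is no shown departure.
- *Off-drug CDLQI scores stay in the analysis.* SAP 5.1 already treats efficacy data collected more than 33 days after the last dose as missing. What remains falls within one dosing interval plus the visit window.
- *Week 20 withdrawal biases the Week 16 result.* It cannot. Nor does it affect any summary up to and including Week 20. The two problems are separate and usually run in opposite directions.
- *The effect is large.* The sizes rest on assumed rates. SAP 5.6 expects few participants not to enter the extension, which points to the lower rows of the Week 20 calculation (small w).

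More can be said for the plan. The LOCF switch is disclosed, and an observed-case sensitivity analysis is planned. SAP 5.1 displays denominators, so attrition is visible. Baseline is carried only when no post-Baseline CDLQI exists. The protocol itself foresaw that multiple imputation might not converge. SAP Section 2 makes every analysis descriptive.

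These points limit the size and the stakes. They do not align LOCF with the stated estimand. A visible denominator does not make a retained-only summary represent the randomized group, and disclosing one change does not disclose the other.

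**Conclusion.** The concern holds in two separate parts.

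1. LOCF, with Baseline eligible, estimates the hypothetical Week 16 CDLQI change only if scores do not change after the last observation, which the documents never assert. Otherwise it usually understates improvement, and the 95% CI omits imputation uncertainty. For 1 to 4 discontinuers of 20, attenuation is 0% (plateau) to 20% (Baseline carried for 4). On the assumed trajectory it is 0.45 to 0.85 points, depending on whether the first visit after the last dose is attended.
2. Observed-case PASI score and change and CDLQI 0/1 depart from Protocol 9.3.3, and Appendix 6.2 does not list the departure. After Week 20 these summaries describe retained participants and usually overstate benefit. For CDLQI 0/1 with 12 later responders of 20, the excess is 3.2 points with 1 removed and 15.0 with 4.

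The text conflicts are certain; the sizes are not, because discontinuation and removal rates are unknown. These are secondary or other endpoints, without testing, in a study whose primary endpoint is PK. The changes should be made, but nothing here threatens the primary objective.

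**What to change.** - **Week 16 CDLQI:** restore the protocol's multiple imputation as the main analysis, by dose group over Weeks 0, 4, 8, 12 and 16, with the protocol's observed-case fallback if the model does not converge. Keep LOCF as a sensitivity analysis.
- **CDLQI 0/1 over time:** make NRI in the Randomized Set the main analysis and show observed-case as supportive.
- **PASI score and change over time:** impute as Protocol 9.3.3 states, or label visits after Week 20 as retained participants only.
- **Appendix 6.2:** list any observed-case departure from Protocol 9.3.3 that remains.

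The cost is SAP wording and a little standard programming, with no change to study conduct. Long-term figures would look slightly less favourable. At about 20 per group the imputation model may fail to converge, which the fallback covers.

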5.4.1.3 Sensitivity Analysis

The OC analysis will serve as the sensitivity analysis for the secondary efficacy endpoints (PASI90 response at Week 16, PASI75 response at Week 4, IGA0/1 response at Week 16, and CDLQI total score change from baseline to Week 16) to assess the impact of missing value on the main imputed analysis.

The following analysis will also be performed as a sensitivity check:

- Separate summary of the secondary efficacy endpoints based on the PK-PPS

5.5 Other Endpoints Analysis

5.5.1 PASI50 / PASI75 / PASI90 / PASI100 response over time

Other PASI response variables, including PASI50, PASI75, PASI90, and PASI100, will be derived and analyzed using the same methods outlined in Section 5.4.1.2. The number and percentage of PASI responders will be reported by dose group for each parameter at each assessed timepoint.

In addition, the number and percentage of participants who achieve the absolute scores of PASI ≤ 1 , ≤ 2 , ≤ 3 , and ≤ 5 at each time point will be summarized for the OC.

5.5.2 PASI change from baseline

The PASI score values and change from Baseline will be summarized descriptively for each timepoint for the OC.

In addition, the value, change, and percent change from Baseline of percent BSA involvement will be summarized descriptively for each timepoint by dose group in the OC.

5.5.3 IGA response over time

The number and percentages of IGA 0/1 and IGA 0 responders at each time point will be reported for each dose group using the same methods outlined in Section 5.4.1.2.3.

5.5.4 Scalp IGA response over time

A static IGA for scalp PSO (Table 5–4) will be completed by the investigator to assess disease severity on the scalp. Scalp lesions will be assessed in terms of clinical signs of redness, thickness, and scaling on a 5-point scale using Table 5–4. This is the same scale with corresponding descriptors used for the overall IGA but will be specific to the scalp. Only participants with a scalp IGA score > 0 at Baseline will have the scalp IGA evaluated.

Scalp IGA response variables will be defined and derived similar to IGA. Scalp IGA 0/1 response is defined as clear [0] or almost clear [1] with at least a 2-category improvement from Baseline. For analysis purposes, the evaluation of scalp IGA will be limited to study participants with a Baseline scalp IGA of at least 2.

Scalp IGA response will be summarized for number and percentages by dose group at each timepoint.

Table 5–4: Scalp IGA

Score	Short Descriptor	Detailed Descriptor
0	Clear	Scalp has no signs of PSO; post-inflammatory hyperpigmentation may be present
1	Almost clear	Scalp has no thickening; normal to pink coloration; no to minimal focal scaling
2	Mild	Scalp has just detectable to mild thickening; pink to light red coloration; predominately fine scaling

Score	Short Descriptor	Detailed Descriptor
3	Moderate	Scalp has clearly distinguishable to moderate thickening; dull to bright red, moderate scaling
4	Severe	Scalp has severe thickening with hard edges; bright to deep dark red coloration; severe/coarse scaling covering almost all or all lesions

5.5.5 CDLQI (total score) change from baseline over time

The absolute value, change and percent change from Baseline for CDLQI total score to each assessed post-Baseline timepoint will be summarized descriptively including n, mean, median, SD, min/max, and lower/upper quartiles in each dose group.

5.5.6 CDLQI 0/1 response over time

The number and percentage of participants who have a CDLQI total score of 0 or 1 will be reported for each time point and by dose group for OC only.

5.5.7 Efficacy and PK relationship

An analysis, based on the Initial Treatment Period, will be conducted to investigate the relationship between plasma bimekizumab exposure and the efficacy variables (PASI response, PASI75, PASI90, IGA 0/1).

This analysis will be described in a separate analysis plan and reported separately.

5.6 Safety Analysis

Safety variables will be analyzed for all study participants in the SS (for the Initial Treatment Period and combined Initial Treatment Period and OLE Period when needed), and in the OLS (for the OLE Period). In general, safety data that are collected within 140 days of the last study drug dose (covering the 20-week SFU Period) will be attributed to the period in which the participant was before initiating the SFU Period and will be analyzed according to the most recent dose prior to or at the time of the collection.

By-visit tables summarizing safety data should include the SFU visit for the ITP + OLE and OLE summaries. However, SFU should not be included in by-visit safety tables for the ITP alone, since only a few participants will not enter the OLE.

